Test-Case Protocol

Version 2, July 31, 2020

R2-B5 -Synthetic Mid-Urethral Slings for Stress Urinary Incontinence in Women

Protocol

National Evaluation System for health Technology coordinating center (NESTcc) ID

Number: [R2-B5]

Lead Principal Investigator: [[name], MS, MPH]

Sponsor: [FDA]

Funded by: Center for Devices and Radiological Health – FDA

Version Number: 2.0

Date: 31 July 2020

TABLE OF CONTENTS

PROTOCOL SYNOPSIS	4
1. INTRODUCTION	6
1.1 RATIONALE & BACKGROUND	6
2. STUDY COLLABORATORS	8
2.1 CONTRIBUTING INSTITUTIONS & ROLES	8
3. STUDY OBJECTIVES	9
4. STUDY DESIGN	10
5. TARGET POPULATION	11
6. STUDY PROCEDURES	11
6.1 STUDY DURATION AND TIMELINE	13
6.2 PROTOCOL DEVIATION HANDLING	13
7. STUDY OUTCOMES	13
8. DATA QUALITY	13
8.1 DATA COLLECTION AND MANAGEMENT	14
8.2 MONITORING PLANS	15
9. STATISTICAL ANALYSIS PLAN (SAP)	15
9.1 STATISTICAL METHODS	15
10. STUDY ADMINISTRATION	15
10.1 CONSENT AND HIPAA AUTHORIZATION REQUIREMENTS	15
10.2 RISK/BENEFIT ASSESSMENT	16
11. RESULTS DISSEMINATION	16
12. REFERENCES	17
13. APPENDICES	19

PROTOCOL SYNOPSIS

Protocol Number: Protocol Date:	R2-B5 07/31/2020
Test-Case ID/Title:	Synthetic Mid-Urethral Slings for Stress Urinary Incontinence in Women
Investigator(s): Study Description:	[name], MS, MPH This project seeks to better understand the safety of mesh mid-urethral slings used for stress urinary incontinence by leveraging electronic health record data. The FDA intends on incorporating these data into its growing portfolio of evidence in order to help support regulatory decision making on level of risk for these procedures and recommendations around use of synthetic mesh for this indication. This study has the potential to increase medical knowledge regarding these devices. A detailed schematic describing all assessments is included in Section 6, Study Procedures .
Summary and Objectives:	The objectives of this project are to assess the capacity of routinely collected electronic health record data to be used to evaluate mid-term (>1 years) to long-term (>2 years) adverse events following transvaginal synthetic surgical mesh implantation (mid-urethral slings) for female stress urinary incontinence (SUI).
Study Design:	This project will be a multi-site retrospective cohort analysis of patients undergoing surgery for the indication of stress urinary incontinence for mid-term outcomes (1 year and greater) and long-term (2 years and greater) among both those with and without trans-vaginally placed synthetic mid-urethral slings (MUS).
Endpoints:	 This project seeks to provide a proof of concept for post-market medical device surveillance utilizing electronic health record data, in a use case of substantial public health safety interest to the FDA, patients, and health care providers: mid- and long-term adverse outcomes related to synthetic surgical mesh implantation for stress urinary incontinence. In pursuit of this goal, this proposal will: Assess data element availability among key covariates and exposures among patients undergoing surgery for stress urinary incontinence. If data are available, to assess rates of outcomes of re-operation for SUI, mesh erosion, re-operation for mesh revision or removal, chronic pain either as a new or worsening pain or requiring re-operation and voiding symptoms either as a new symptom or requiring re-operation, each with extended surveillance windows
	 after surgery. Provide a report of additional data elements important to conduct future device post-market surveillance in implantable devices for this indication, extrapolating to other device domains.

- 4) Lastly, if the data quality and volume are sufficient, we will develop a risk prediction model for the risk of the each of the outcomes stated above among patients receiving mesh for SUI.
- Statistical Methods: Each of the outcomes, exposures, and covariates will be summarized in aggregate for each site and a summarization and report will be provided to characterize the data at each site. Stratified reporting of those receiving surgery for SUI with synthetic mesh overall, SUI with synthetic mesh implantation by surgical approach, and SUI without mesh will be performed.

Next, if the characterization of the data is sufficient for the task, we will pursue a Cox proportional hazards model analysis, with each of the outcomes assessed from the time of the surgery as a time-to-event. We will censor the time-to-event analysis with death or loss to follow-up, defined as a time period >2 years from last applicable encounter of primary care, Obstetrics & Gynecology, or Urology. The models will first be developed at each institutional separately using LASSO Cox to predict time to event for each of the outcomes of interest. We will use the variables retained in any of the individual site models, and develop a Cox model using the method described by Lu and colleagues (WebDISCO) that uses a distributed analysis approach to obtain an exact model solution without sharing case level data (only intermediate and aggregate model coefficients and matrices)¹. This method is being used to protect patient data by processing it at the local institutions and only sharing intermediate modeling statistics (aggregates) between sites.

Because bootstrapping combined with the distributed analysis method would be computationally intensive, we will utilize 10-fold cross validation across all sites for internal validation of the risk model. We assessed overall discrimination using Harrell's concordance statistic (C-statistic). To provide calibration assessments, we will also evaluate the model at fixed time points of 1 year and 2 year for each outcome using the AUC and the Estimated Calibration Index (ECI). The ECI looks at the squared difference between the predicted probability and an estimated observed probability, ranging between 0 and 100, with 0 meaning perfect calibration. Additionally, we will graphically analyze calibration by investigating the smoothed observed-to-predicted probability plot.

Target Population:All women aged 18 or greater undergoing transvaginal surgery for stress
urinary incontinence with or without mid-urethral mesh sling implantation
are eligible for inclusion in the EHR data. Determination of the appropriate
mesh exposure during surgery will be determined through administrative
CPT procedure codes, as defined in the appendix. No exclusions will be
applied based on race or ethnicity. As a separate sensitivity analysis to
reduce potential lack of outcome ascertainment, we will exclude all
patients that do not also have continuity of care within the data site,
defined as requiring at least one outpatient medicine specialty or relevant
(Obstetrics & Gynecology, Urology) sub-specialty encounter in the 12
months prior to implantation. For this sensitivity analysis, we will also
exclude patients with prior pelvic organ prolapse or stress urinary
incontinence surgeries. As an additional comparator population, we will

Synthetic Mid-Urethral Slings for Stress Urinary Incontinence in Women	
Protocol 1	

	identify all those who underwent a procedure for SUI but did not receive mesh implantation.
Description of Sites/Facilities:	The Participating Sites for this Study include Vanderbilt University Medical Center, Lahey Hospital & Medical Center, Mayo Clinic, Weill-Cornell, and Yale New Haven Health System. In addition, as a data quality validation check, we will have access to a manually collected and curated 3,472 patient case series at Mayo Clinic from 2002 to 2012 of patients that underwent surgery for incontinence ² . For the routine EHR data sources, the valid dates will be from 2010 to the most recently available data.
	As a preliminary assessment of data volume, each site queried their data for CPT 57288 sling operation for stress incontinence. VUMC had a total of 6,106 from 2010-2018, and an average of ~500 cases a year for the last 4 years. Mayo Clinic had a total of 5,413 cases from 2010-2018, and an average of ~500 cases a year for the last 4 years. Weill-Cornell had 887 cases from 2010 to 2019, and an average of 150 procedures a year over the last 4 years. Yale New Haven Healthcare System has data from 2013-2018, and about 170 procedures in the most recent 6-month period. Lahey Clinic had 108 surgeries in 2018, and an average of 84 procedures a year over the last 4 years.
Description of Study Intervention:	This is an observational study design, and there are no direct interventions for patients, thus a Data and Safety Monitoring Plan is not required, and a Data and Safety Monitoring Board is not required.
Study Duration:	1 year, Start Date 02/17/2020, End Date 03/15/2021.
Duration of Data Captured:	2010-2019 in EHR Data

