1. INTRODUCTION

1.1 RATIONALE & BACKGROUND

Urinary incontinence, defined as involuntary loss or leakage of urine, is a common problem that affects women more often than men, with prevalence increasing with age³. There are several types of urinary incontinence, with distinct differences in pathophysiology between men and women^{4,5}. Incontinence in women is typically related to dysfunction of the bladder or pelvic floor muscles through functional or mechanical changes over time resulting from pregnancy, childbirth, in menopause, or other conditions⁵. There are two main subtypes of urinary incontinence, stress and urge, and a third type that can be defined as mixed symptoms of both⁶. In urge incontinence, leakage occurs with a sudden intense need to void, and in stress incontinence, leakage is associated with physical exertion, coughing, sneezing, or other activity.

Urge incontinence mainly involves bladder dysfunction, either detrusor overactivity, poor detrusor compliance, or bladder hypersensitivity. This is important because treatment pathways are distinct as well. Unlike urge incontinence, two common mechanisms for stress urinary incontinence (SUI) are either urethral hypermobility resulting from loss of support of the bladder neck and urethra, and weakness of the urinary sphincter itself⁵. The hammock hypothesis is supported as the pathophysiological explanation for SUI associated with hypermobility⁷. Weakness of the sphincter itself can occur after trauma, repeated surgeries, neurological disease, aging, or systemic muscular atrophy. The Integral theory expands on the hammock hypothesis to include an understanding that stress and urge symptoms may have multiple reasons for generating a lax vagina, which impairs the mediation of muscle movements involved in

Version 2.0 [15 July 2020]

bladder neck function as well as inducing urgency through stretch receptors in the urethra and bladder neck⁸. Although all SUI treatments are used for both types, they are more successful among those with urethral hypermobility, than for isolated sphincter weakness⁹.

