5. TARGET POPULATION

Inclusion criteria:

- All women aged 18 or greater undergoing transvaginal surgery for stress urinary incontinence (index surgery) with or without mesh implantation
- EHR-Based study date range 2010-2019
- Inpatient or outpatient visit

Exclusion criteria:

- No primary care, ob/gyn, or urology visits in the year prior to the surgery
- Prior pelvic organ prolapse surgery
- Prior stress urinary incontinence surgery
- Prior surgery diagnosis of a urethral diverticulum ICD-9-CM code 619.0 or any urinary-genital tract fistula (codes 599.1 and 599.2) in the 90 days prior to the index surgery.

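### The one sensitivity analysis for missed outcomes also excludes women with prior surgery, so its result cannot be attributed to ascertainment; Section 5 already lists both restrictions as exclusions

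*Protocol*

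**What the plan says.** The synopsis, under Target Population, makes all adult women having transvaginal surgery for stress urinary incontinence (SUI) eligible. It then describes a separate sensitivity analysis whose purpose is to "reduce potential lack of outcome ascertainment, we will exclude all" patients without continuity of care at the site. Continuity is "defined as requiring at least one outpatient medicine specialty or relevant" sub-specialty encounter in the 12 months before implantation. Nothing is required after surgery. The second restriction is added to the same analysis: "months prior to implantation. For this sensitivity analysis, we will also" is followed by "exclude patients with prior pelvic organ prolapse or stress urinary" incontinence surgeries. No step applies the continuity restriction alone.

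Section 5 lists among the exclusion criteria of the study itself: "No primary care, ob/gyn, or urology visits in the year prior to the surgery", "Prior pelvic organ prolapse surgery" and "Prior stress urinary incontinence surgery". These are essentially the synopsis restrictions, but here they define the target population.

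Sections 6 and 8.1 both acknowledge substantial ascertainment bias and defer its treatment to the study design and methods. Section 4 (Study Design) names no further sensitivity analysis.

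**The concern.** A sensitivity analysis answers a question only if it changes the feature in question and leaves the rest alone. Here the question is whether events are missed because women receive later care elsewhere. Requiring an established link to the site bears on that. Whether a woman had earlier prolapse or SUI surgery bears mainly on her risk, and so on the rate that would be seen even with perfect capture.

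With both changes made at once, agreement with the main rate may mean that few events are missed, or that better capture and a lower-risk case mix have offset each other. A difference may likewise reflect case mix alone. Readers would naturally take agreement as reassurance about outcome loss, and the results are intended to inform regulatory decisions on these devices.

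The contradiction with Section 5 adds a second way to obtain an uninformative null: the two cohorts may be almost the same women.

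**Working it through.** The protocol gives no expected rate, prior-surgery share or capture proportion for this analysis, so there is no planned figure to reproduce. A simple mixture model shows what the combined run can and cannot reveal.

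**Inputs**
- R: event risk in women without prior surgery. Set to 5.5% purely as a scale, borrowed from the five-year re-operation figure of a UK study of 95,057 women cited in Section 1.1. It cancels from every ratio.
- q: share with prior surgery. Assumed 10-20%.
- RR: risk ratio for prior surgery. Assumed 1.5-2.5.
- k0: share of events captured in the main cohort. Assumed 70-80%.
- k1: share captured with continuity. Assumed 85-95%.

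None of q, RR, k0 and k1 is in the documents. Prior surgery and continuity are taken as independent.

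**Formulas**, with m = 1 + q(RR - 1)
- Main observed rate: R × m × k0
- Continuity only: R × m × k1, ratio to main k1/k0
- No prior surgery only: R × k0, ratio 1/m
- Both, as the synopsis plans: R × k1, ratio (k1/k0)/m

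**One worked case** (q = 0.15, RR = 2, k0 = 0.80, k1 = 0.90, so m = 1.15)

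| Analysis | Observed rate | Ratio to main |
|---|---|---|
| Main | 0.055 × 1.15 × 0.80 = 5.06% | 1.00 |
| Continuity only | 0.055 × 1.15 × 0.90 = 5.69% | 1.13 |
| No prior surgery only | 0.055 × 0.80 = 4.40% | 0.87 |
| Both | 0.055 × 0.90 = 4.95% | 0.98 |

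Here 20% of events are missed in the main cohort, and the combined run moves by 2%.

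**Full range, every stated value crossed**
- k1/k0 runs from 0.85/0.80 = 1.06 to 0.95/0.70 = 1.36. This is the continuity-only ratio, always above 1.
- m runs from 1 + 0.10 × 0.5 = 1.05 to 1 + 0.20 × 1.5 = 1.30.
- The combined ratio runs from 1.0625/1.30 = 0.82 to 1.357/1.05 = 1.29, straddling 1.

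**Exact offset.** The combined ratio is 1 when k1/k0 = m. If capture is complete with continuity, the share missed at that point is 1 - 1/m. For q = 0.15 and RR = 2 this is 1 - 1/1.15 = 13.0%. Continuity alone would then show 1.15.

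**The reverse error.** With no missed events (k0 = k1 = 1) and the same q and RR, the combined ratio is 1/1.15 = 0.87: a shift with nothing wrong in ascertainment.

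**When the effects do not oppose.** At RR = 1 the prior-surgery exclusion changes nothing and there is no masking. At RR = 0.8, with q = 0.15 and capture 0.80 rising to 0.90, m = 0.97 and the combined ratio is 1.125/0.97 = 1.16, so both restrictions push upward.

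**If Section 5 governs.** The main cohort already has both restrictions, so the sensitivity cohort is nearly the same set and the ratio is about 1 whatever is missed.

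**The case against.** A reader might infer that the two restrictions push the rate in opposite directions and tend to cancel. The documents do not support that. They give no outcome rate by prior surgery or by continuity. The nearest text is in Section 1.1: "Weakness of the sphincter itself can occur after trauma, repeated surgeries, neurological disease, aging, or systemic muscular atrophy", followed by the remark that treatment works less well for isolated sphincter weakness. That is indirect, and bears on re-operation and recurrence more than on erosion or pain. The upward effect of continuity is also assumed, because one pre-operative visit does not guarantee follow-up. On a three-point grid over the ranges above, 15 of 81 scenarios (19%) lie within 3% of no change and 49 (60%) show a rise above 3%. Offsetting is possible, not typical.

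The split between capture and case mix is not clean either. The Appendix counts sling revision or removal as an outcome, which could concern an earlier sling, and it warns that voiding symptoms may be hard to tell from pre-existing ones. Excluding prior surgery may therefore improve outcome attribution, and requiring continuity may change case mix.

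The protocol also has other checks: chart review of 50 to 100 cases per site and the curated Mayo series. These are partial. A site's own charts would not ordinarily show care given elsewhere, and the Mayo comparison covers one site.

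Stepwise reporting could be left to a SAP that is not shown. But the synopsis does more than stay silent: it defines a single analysis carrying both restrictions, and Section 5 contradicts it on which population is main. These objections limit the claim about direction and size; the problem of attribution stands.

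**Conclusion.** The combined analysis cannot be read as a test of outcome ascertainment. Under the synopsis, neither agreement nor a difference can be attributed to missed events unless prior surgery has no effect on the outcome. Under Section 5, agreement is close to guaranteed.

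The size rests wholly on assumed inputs. Over the ranges shown, the combined ratio straddles 1 while the continuity-only ratio stays above it. That illustrates what can happen and does not estimate what will. The change is worth making because it costs little and the protocol describes no other sensitivity analysis for outcome loss.

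**What to change.** 1. Reconcile the synopsis with Section 5 and state which population is main. If the Section 5 exclusions stand, say that the sensitivity comparison needs a wider cohort without them.
2. Against a cohort without these restrictions, run (1) continuity of care only, (2) no prior prolapse or SUI surgery only, and (3) both.
3. Base the statement on ascertainment on run (1) and report run (2) as a case-mix check. State that continuity is defined only by a pre-operative visit, so it does not ensure follow-up and may itself shift case mix.

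The cost is a sentence or two in the protocol and two extra runs of existing code at each site, with no new data.

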1. INTRODUCTION

1.1 RATIONALE & BACKGROUND

Urinary incontinence, defined as involuntary loss or leakage of urine, is a common problem that affects women more often than men, with prevalence increasing with age³. There are several types of urinary incontinence, with distinct differences in pathophysiology between men and women^{4,5}. Incontinence in women is typically related to dysfunction of the bladder or pelvic floor muscles through functional or mechanical changes over time resulting from pregnancy, childbirth, in menopause, or other conditions⁵. There are two main subtypes of urinary incontinence, stress and urge, and a third type that can be defined as mixed symptoms of both⁶. In urge incontinence, leakage occurs with a sudden intense need to void, and in stress incontinence, leakage is associated with physical exertion, coughing, sneezing, or other activity.

Urge incontinence mainly involves bladder dysfunction, either detrusor overactivity, poor detrusor compliance, or bladder hypersensitivity. This is important because treatment pathways are distinct as well. Unlike urge incontinence, two common mechanisms for stress urinary incontinence (SUI) are either urethral hypermobility resulting from loss of support of the bladder neck and urethra, and weakness of the urinary sphincter itself⁵. The hammock hypothesis is supported as the pathophysiological explanation for SUI associated with hypermobility⁷. Weakness of the sphincter itself can occur after trauma, repeated surgeries, neurological disease, aging, or systemic muscular atrophy. The Integral theory expands on the hammock hypothesis to include an understanding that stress and urge symptoms may have multiple reasons for generating a lax vagina, which impairs the mediation of muscle movements involved in

Version 2.0 [15 July 2020]

bladder neck function as well as inducing urgency through stretch receptors in the urethra and bladder neck⁸. Although all SUI treatments are used for both types, they are more successful among those with urethral hypermobility, than for isolated sphincter weakness⁹.

As noted above, SUI is a common condition among women, and negatively impacts patient quality of life, with an estimated 50% of patients experiences some symptoms during their lifetime¹⁰. Because of the impact of SUI, many women seek treatment for these symptoms, and first line treatments of symptoms includes lifestyle changes, fluid intake restriction, pelvic floor exercises, and vaginal pessaries⁴. When these are inadequate, implantation of a mesh mid-urethral sling is a recognized minimally invasive surgical treatment for SUI^{11,12}.

An estimated 1 in 5 women will undergo surgery for pelvic organ prolapse (POP) or SUI by age 80 in the US, and approximately 260,000 underwent surgical repair for SUI in 2010^{13,14}. While there are multiple types of surgery, the most common is a trans-vaginal approach that uses one of four routes to conducting the procedure, depending on circumstances and provider and patient preferences: Retro-Pubic (RPMUS), Trans-Obturator (TOMUS), Single Incision (SIMUS), and Adjustable Sling (AMUS). Surgical implantation of mesh to create mid-urethral slings (MUS) to relieve these symptoms has been reported to have one-year curative results for TOMUS from 62-98% and for RPMUS from 71% to 97%^{11,15}. Older studies have shown lower success rates for SIMUS vs RPMUS and TOMUS¹⁶.

Across all approaches, these implanted medical devices have also been shown to have a number of adverse outcomes, including chronic pain¹⁷, urethro-vaginal fistula¹⁸, voiding dysfunction^{19,20}, and mesh erosion^{21,22}. Voiding dysfunction can develop in 3-30% of patients after RPMUS and 0-16% after TOT²³. Because of these adverse outcomes, reoperation rates can approach 8-9%²⁴. Overall, these procedures were thought to have reasonable success and adverse event profiles for outcomes out to one-year post-operation, but data beyond this window was sparse.

However, by the mid-2000's, a growing number of adverse event reports had been submitted to the MAUDE FDA database related to trans-vaginal synthetic mesh products used for these indications. During 2005-2010, MAUDE received 1371 reports of injury, death, and malfunction of mesh for SUI treatment, related to mesh erosion, pain, infection, recurrence of urinary symptoms, and organ perforation, along with a 5-fold increase in MAUDE reporting rates in 2008-2010 compared to 2005-2007. While these numbers increased scrutiny surrounding these devices, a lack of denominator data and a reliance on voluntary reporting that is sensitive to FDA and press scrutiny limit the interpretability of these findings.

Risk assessments around synthetic surgical mesh for SUI remains uncertain for some outcomes extending beyond one year²⁵. [name] and colleagues evaluated a New York State prospective registry (SPARC) that included all surgeries and evaluated 41,604 women undergoing mesh implantation for pelvic organ prolapse or stress urinary incontinence. Among the 22,252 women undergoing surgery for SUI, 1.6% of them had mesh erosions that required intervention²². In one UK study, overall re-operation rates were only 3.2% among mid-urethral sling procedures for SUI after a median 2.8 years of follow-up²⁶. In a private US claims database, the cumulative re-operation rate was 14.5% after a median 9 years of follow-up²⁷, with sling revision/removal at 3.7%²⁸. Other small studies in non-US populations have shown low rates of long-term complications (1-3%)²⁹. A recent UK study among 95,057 women and a median follow-up time of 5.5 years found that risk of re-operation was 2.6% at 1 year, 5.5% at 5 years, and 6.9% at 9 years³⁰. More specifically, mesh removal rates were 3.3% at 9 years in this population. Another UK study among 92,246 patients with first time mesh implantations for SUI found a 5-year complication rate of 9.8%³¹. A Canadian study of 59,887 women found ~3.5% may require mesh removal or revision within 10 years of initial surgery³².

There have also been some systematic reviews and meta-analyses done attempting to further understand the complications in this population. In 2015, a systematic review of studies with a follow-up of 36 months for TOMUS and 60 months for RPMUS were searched and studies comparing the two were

included (49 studies, 11 RCT, 38 retrospective cohort studies)³³. The studies had a complication rate of 193% for RPMUS and a complication rate of 23.8% in TOMUS surgeries. The two approaches had similar objective cure rates, but TOMUS had a lower subjective cure rate than RPMUS. In 2017, a review was published evaluating 11 RCTs and 5 non-RCTs evaluating the long term efficacy and safety of MUS in women³⁴. There was a total of 1,200 patients across 11 RCTs with individual surgical approach populations in each trial being in the 30-299 range. Ascertainment for the RCTs were good and showed no safety or efficacy differences between approaches but were limited in size, and the non-RCTs were similarly limited in size (5206 patients across 5 studies). The most recent review, in 2019, evaluated a total of 175 RCTs with 21,598 women, and noted that most studies had high or unclear risk of bias across all Cochrane domains³⁵. A network metanalysis was done from 105 trials that reported cure and 120 trials that reported improvement of symptoms, and across the 4 common surgical approaches for MUS. The key findings from this meta-analysis was that RPMUS, TOMUS, traditional sling, and open colposuspension were more effective than other procedures for SUI, but that data on long term effectiveness and adverse events were limited, particularly around comparison between MUS and non-MUS procedures. Other relevant articles are referenced here as well, but almost all of these also cite limitations in sample size, data bias collection, and evidence limitations³⁶⁻⁴¹.

The FDA is very interested in measuring the risk of mesh use for SUI for longer outcomes >1 year within electronic health record data, which are collected for routine care and can be accessed for a variety of surveillance activities. For this reason, NESTcc was approached by the FDA to engage in a collaborative consortium to pursue these concerns, and an RFP was released to study this within an electronic health record environment in which it is hoped that longer term outcomes can be ascertained. Multiple academic medical centers, including Vanderbilt University Medical Center, Yale New Haven Health System, Weill-Cornell, Mayo Clinic, and Lahey Hospital & Medical Center, were recruited to collect and analyze patient data regarding mesh implantations for SUI for the outcomes of re-operation, mesh erosion, all-cause chronic pain, and continued voiding symptoms that occur past 1 year after the surgery.

